Fingolimod also causes a dose-dependent reduction in peripheral lymphocyte count to 20%-30% of baseline values because of reversible sequestration of lymphocytes in lymphoid tissues. Fingolimod may therefore increase the risk of infections, some serious in nature. Additionally, in clinical trials there have been rare cases of posterior reversible encephalopathy syndrome (PRES) reported in patients receiving fingolimod. Dyspnea was reported in 9% of patients receiving fingolimod 0.5 mg and 7% of patients receiving placebo in MS placebo-controlled trials. Also, in 2-year placebo-controlled clinical trials, elevation of liver transaminases to 3-fold the upper limit of normal (ULN) or greater occurred in 14% of patients treated with fingolimod 0.5 mg and 3% of patients on placebo. Elevations 5-fold the ULN or greater occurred in 4.5% of patients on fingolimod and 1% of patients on placebo. Based on animal studies, fingolimod may cause fetal harm. Fingolimod also increases the risk of macular edema, the risk of which is increased in patients with a history of uveitis and patients with diabetes mellitus. In 2-year, double-blind, placebo-controlled studies in patients with multiple sclerosis, macular edema with or without visual symptoms occurred in 1.5% of patients (11/799) treated with fingolimod 1.25 mg, 0.5% of patients (4/783) treated with fingolimod 0.5 mg and 0.4% of patients (3/773) treated with placebo.

Rationale of Study Period

Two months was chosen as the treatment period because it is an adequate duration for an initial safety assessment in schizophrenia of early emerging adverse events. In addition, significant effects in MS patients were observed as early as two months post randomization (16). Further, Garver et al (25) reported improvement in DTI-determined white matter integrity in patients with schizophrenia who responded to antipsychotic drug therapy in only 28 days. Thus, if fingolimod has a large effect in improving the symptoms of schizophrenia, it may be detected in a two month study of 40 subjects.

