3.0 Specific Aims

The **primary aims** of this clinical study are to 1) assess the safety of fingolimod in subjects with schizophrenia being treated with antipsychotic drugs, and 2) determine if fingolimod compared to placebo results in symptomatic improvement as measured by reductions in PANSS total score.

Secondary aims include assessment of the effects of fingolimod versus placebo on memory, cognition, positive and negative symptoms, and plasma cytokine levels in addition to gathering preliminary data on the effects of fingolimod on DTI-derived FA and other MRI indices.

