4.0 Study Design

This will be a single site safety and proof of concept study conducted at the Indiana University Psychotic Disorders Program. Forty subjects with schizophrenia or schizoaffective disorders with suboptimally treated symptoms (despite previous and/or current antipsychotic medication exposure) (39) will be randomized 1:1 to double-blind treatment with fingolimod or matched placebo for duration of 8 weeks.

All subjects will be admitted to the Indiana Clinical and Translational Sciences Institute Clinical Research Center (CRC) and remain hospitalized for the first 24 (+/- 2) hours post initial dose of study medication. The CRC is located in Indiana University Hospital and has 24 hour staffing with nurses skilled in conducting Phase 1 and Phase 2 investigational drug studies.

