10.0 Criteria for Rescreening, Repeat Assessments, and Discontinuation

Repeat Assessments

Screening assessments can be repeated within the screening window under the same screening number with the exception of eligibility criteria related rating scales/questionnaires. Subject diagnosis confirmation will not be repeated.

Rescreening

Subject who screen fail may be rescreened one time, under a new screening number. If a subject is rescreened, all screening assessments (with the exception of the diagnosis confirmation) must be repeated and the stability criteria timelines must be met.

Discontinuation

Subjects will be discontinued under the following circumstances:

1. Within the first two weeks of treatment, subjects with an interruption of treatment of one day or more
2. Within the third and fourth week of treatment, subjects with an interruption of treatment of more than seven days
3. Subjects who have an elevation of liver transaminase levels >3 times the ULN while on study medication
4. Subjects who develop moderate or severe renal impairment as defined by CrCl <60 ml/min (measured by the Cockcroft-Gault equation) while on study medication
5. Female subjects who become pregnant while on study medication
6. Subjects who develop a serious infectious disease while on study medication
7. Subjects who develop macular edema or uveitis while on study medication
8. Any subject who requires pharmacologic intervention for symptomatic bradycardia after the second dose of study medication or who continues to experience bradycardia or who demonstrates any other new, serious cardiac pathology 24 (+/-2) hours after the second dose of study medication will be discontinued from the study
9. Subjects who require an increase in their dose of antipsychotic medication or the addition of a new antipsychotic medication
10. Subjects who require treatment with any excluded concomitant medications (See Attachment 2)

If subjects discontinue from the study, discontinuation assessments will be at the discretion of the principal investigator.

A subject may withdraw from the study medication at any time at his/her own request, or may be withdrawn at any time at the discretion of the principal investigator for safety, behavioral, or administrative reasons.

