16.0 Statistical Considerations

Analyses

In terms of the power to detect a significant effect of this molecule, there are no known calculations with schizophrenia patients. However, an extension phase of a MS registration trial found that patients on fingolimod demonstrated rapid anti-inflammatory responses in relatively small samples (< 35 subjects per dosing arm) (16). In addition, Garver et al (25) examined myelin integrity in schizophrenia and found significant improvement in white matter integrity utilizing a small sample (N=8) of antipsychotic drug responsive schizophrenic patients. Given the above findings, it is reasonable to assume a medium (0.50) to large effect size (0.80) will be observed. Therefore, with a sample size of 40 patients, we could detect a significant effect of treatment (between the fingolimod and placebo groups) with statistical power (37) between .3 and .7, utilizing a two-sided independent test and a significance level of 0.05.

Preliminary analyses will consist of descriptive statistics for all outcome variables, including summary statistics, graphical displays of distributions, and spaghetti plots of individual data over time to detect possible data errors. Demographic and clinical characteristics at baseline will be compared between the two randomized groups, using parametric or nonparametric test statistics as appropriate. Variables that show significant differences will be added to the final models as covariates in order to ensure that the observed treatment effects are not spurious or due to demographic confounds. Data

analysis will be *intent to treat* with all data considered usable providing subjects have completed the randomization visit. To minimize the potential for Type I error, all treatment comparisons will be evaluated based on a two-sided significance level of 0.05. Primary and secondary measures will be examined using ANOVA and ANCOVA general linear modeling analyses for measures resulting in ratio data or the Kruskal-Wallis for those measures that produce ordinal data.

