Med/Psych/ Medication History	X															
Demographics	X															
Physical Exam	X															
Vitals	X			X			X	X	X	X	X	X	X	X	X	X
Ophthalmology Exam		X														X
ECG (triplicate, 1 min apart)	X			X			X	X	X	X	X	X	X	X	X	X
CGI-S&I^e	X			X			X	X	X	X	X	X	X	X	X	X
BPRS	X															
PANSS			X				X			X				X		
PSP			X				X	X	X	X	X	X	X	X	X	X
EQ-5D & Quality of Life			X							X				X		
BACS/Trails B			X							X				X		
MRI			X											X		
BFCRS				X										X		
AIMS					X									X		
SAS					X									X		
BARS					X									X		

Visit	1a	1b	2	3a Inpatient	3b ^a Inpatient	3c ^b Inpatient	4	5	6	7	8	9	10	11 ^d /ET	12	13
Day				-1 to -6 hours	0	1	7	14	21	28	35	42	49	56	84	112
Visit Window (days since last visit) ^f			0-30	0-7	NA	NA	5-9	5-9	5-9	5-9	5-9	5-9	5-9	5-9	24-32	24-32
CBC w/ diff	X									X				X		X
CMP	X									X				X		X
TSH	X															
Beta HCG	X															
VZV Titer	X															
HIV test	X															
Hepatitis Panel	X															
Plasma Cytokines				X							X			X		
Magnesium & Calcium	X															
Lipid Panel	X															
HgbA1c	X															
Urine Toxicology	X		X	X				X	X	X	X	X	X	X		
Urine Pregnancy Test	X		X	X				X	X	X	X	X	X	X	X	X
Adverse Event	X		X	X	X			X	X	X	X	X	X	X	X	X
Concomitant Medication	X		X	X	X			X	X	X	X	X	X	X	X	X
Medication Dispensation					X ^c	X		X	X	X	X	X	X	X		
Medication Accountability								X	X	X	X	X	X	X		
Telemetry						X	X									
Hourly Blood Pressure					X	X										

a 3b is the first 24 +/- 2 hours post dose

b 3c will be completed per dosing safety section as outlined in this protocol (if applicable)

c Initial dose will be administered before 12pm

d Visit 11 procedures may be split over a 7 day period

e Only CGI-S will be completed at visit 1a

f: All visits may be split at the discretion of the principal investigator

ATTACHMENT 2

Concomitant Medication Table

Medication	Use prior to Visit 4	Use after Visit 4
Class 1a antiarrhythmic	No	No
Class 3 antiarrhythmic	No	No
Alpha 2 agonists (eg., Clonidine)	No	No
Alpha-adrenergic blockers (eg., doxazosin, terazosin)	Stable dose, no changes or additions	Stable dose, no changes or additions
Anticoagulants	No	No
Antiemetics (eg., metoclopramide, domperidone, other dopamine receptor blockers)	No	No
Antiepileptic mood stabilizers	Stable dose, no changes or additions	Stable dose, no changes or additions
Antihistamines, nonsedating	Yes	Yes
Antihistamines, sedating	Yes ^a	Yes ^a
Antineoplastics	No	No

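### Section 10.0 leaves the exit PANSS to discretion although Attachment 1 schedules it, and section 16.0 names neither a PANSS analysis visit nor a method for missing scores

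*Combined protocol and SAP*

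**What the plan says.** - **Assessments at exit.** Section 10.0, under Discontinuation: "If subjects discontinue from the study, discontinuation assessments will be at the discretion of the principal investigator". In Attachment 1, Visit 11 doubles as the early-termination visit, and PANSS, ECG, CBC and CMP are marked there. Its footnotes allow procedures to be split ("Visit 11 procedures may be split over a 7 day period") but give no leave to omit them.
- **Primary outcome.** Section 3.0 aims to "determine if fingolimod compared to placebo results in symptomatic improvement as measured by reductions in PANSS total score". No visit is named. The PANSS is scheduled at Visit 2 (baseline), Visit 4 (Day 7), Visit 7 (Day 28) and Visit 11/ET (Day 56).
- **Analysis.** Section 16.0 declares intent to treat, "with all data considered usable providing subjects have completed the randomization visit", and then states: "Primary and secondary measures will be examined using ANOVA and ANCOVA general linear modeling analyses for measures resulting in ratio data". Ordinal measures go to Kruskal-Wallis. There is no repeated-measures structure, rule for missing scores, sensitivity analysis or dropout allowance, and no other section supplies them.
- **Who leaves.** Section 10.0 removes subjects who need more antipsychotic treatment (item 9) and those with possible drug effects (items 3, 6, 7 and 8: liver, infection, eye, cardiac). Item 1 covers "Within the first two weeks of treatment, subjects with an interruption of treatment of one day or more". Voluntary withdrawal is allowed at any time.

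**The concern.** Site staff reading section 10.0 and Attachment 1 cannot tell whether an exit PANSS is required. Whether a leaver has one may then depend on a judgement made when the subject is doing badly.

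This matters most before Day 7. Item 1 and item 8 (around the second dose) act early. Items 3-7, 9 and 10 and voluntary withdrawal have no earliest time. Only item 2, which concerns weeks three and four, cannot act before the first post-baseline PANSS. For anyone leaving that early, the ET rating is the only post-baseline score there can be.

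Subjects leaving later do have a Day 7 or Day 28 score, but the plan does not say how it enters the analysis. A completer ANCOVA, a last-score ANCOVA and a repeated-measures model could each claim to follow section 16.0, and they can give different primary results. If leaving tracks symptoms and differs by arm, the contrast moves. More placebo loss from worsening shrinks it; more drug loss among subjects doing badly enlarges it.

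**Working it through.** **Inputs from the documents.** 40 subjects randomised 1:1 (section 4.0), so 20 per arm; standardised effect 0.50 to 0.80, two-sided alpha 0.05, power .3 to .7 (section 16.0).

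**The plan's own figure.** A two-sided t-test with 20 per arm has power 0.338 at 0.50 and 0.693 at 0.80, which agrees with .3 to .7 at one decimal. There is no dropout allowance. If leavers contribute no score, power is 0.308 / 0.645 at 10% loss (18 per arm) and 0.278 / 0.591 at 20% (16 per arm).

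**Assumed, because the documents are silent.** SD 1; true effect 0.50, reached 25% / 60% / 100% by Days 7 / 28 / 56; correlations baseline-D7 .75, baseline-D28 .65, baseline-D56 .60, D7-D28 .80, D7-D56 .70, D28-D56 .85. With baseline as covariate, the standard error is about √[(2/20) × (1 − 0.60²)] = √0.064 = 0.253. Simulation gives about 0.26, and full-data power is 0.48.

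**(a) Loss from worsening.** A subject leaves if Day 28 minus baseline is at least 0.6, 0.9 or 1.2 SD. Estimates are in SD in favour of drug; the full-data value is about 0.50.

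| Loss placebo/drug | Mean number lost of 40 | Completer ANCOVA (power) | Likelihood model, exit after Day 28 PANSS | Likelihood model, exit before it, no ET score | Same, ET score from all leavers |
|---|---|---|---|---|---|
| 23.7/14.2% | 7.6 | 0.418 (0.353) | 0.501 | 0.438 | 0.499 |
| 14.0/7.5% | 4.3 | 0.438 (0.400) | 0.498 | 0.459 | 0.499 |
| 7.5/3.6% | 2.2 | 0.462 (0.429) | 0.497 | 0.470 | 0.496 |

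If, in the early-exit case, only the less-worsened half of leavers is rated, the model gives 0.461, 0.474 and 0.479. Using the ET score as the last score in an ANCOVA gives 0.484, 0.493 and 0.503, with power 0.427, 0.443 and 0.466, still below 0.48.

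The last column is favourable by construction: the ET score entered is the same value that caused the exit. The likelihood columns also assume that everyone has a Day 7 score.

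**(b) Loss on drug unrelated to PANSS, 15%.** No bias; power falls from about 0.48 to 0.44.

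**(c) Loss tied to the unseen Day 56 score.** Unadjusted shift = (difference in missing fraction) × (leaver-stayer gap). Baseline adjustment removes part of it, leaving about 1 − 0.60² = 0.64.
- Drug 30%, placebo 10%, gap 0.66: 0.20 × 0.66 × 0.64 = 0.08. Gap 0.82: 0.20 × 0.82 × 0.64 = 0.10. Simulated completer estimates are 0.582 and 0.599, which agree.
- Reversed loss: 0.428 to 0.400.
- Likelihood model: 0.538-0.543 and 0.469-0.454 respectively, so the bias is reduced but not removed.
- At 20% against 10%, the completer estimate is 0.54-0.55 or 0.45-0.46.
- Type I error of the completer ANCOVA: 0.056-0.066 at 30% drug / 10% placebo, 0.053-0.054 at 20% / 10%, and 0.049 with equal 15% loss.

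**The case against.** The other side has real points. This is a small proof-of-concept study that states its low power openly. It is double-blind ("will be randomized 1:1 to double-blind treatment with fingolimod or matched placebo for duration of 8 weeks"), which limits rating choices that follow the arm. The intent-to-treat sentence opposes a deliberate completer-only analysis. Section 2.0 says a large effect "it may be detected in a two month study of 40 subjects", so Day 56 is the natural reading. The ET column could be read as the procedures available, with section 10.0 giving discretion over which are done. Every dropout rate above is assumed, and the shifts are well inside sampling error.

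All of this limits the size of the problem. It does not settle whether an exit PANSS is required, say how a Day 7 or Day 28 score is used, or supply a method for a missing Day 56 score.

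A reader might infer that the exit PANSS and the new model are both needed in every case. That is not shown. When the same subjects leave after the Day 28 PANSS, the likelihood model alone returns about 0.50. The ET score matters for earlier exits. Early cardiac or interruption exits that are unrelated to PANSS cost power but add no bias.

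A reader might also infer that leavers go without safety follow-up. The documents do not support that: adverse-event follow-up (section 14.0), the eye examination and the symptom-triggered liver tests (section 9.0) cover part of it.

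**Conclusion.** The point holds at minor to should-fix level. Section 10.0 and Attachment 1 conflict on the exit PANSS and must be reconciled. Section 16.0 does not say how its intent-to-treat promise is kept when the Day 56 score is missing.

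Under the assumed worsening-related loss, the completer estimate is about 0.04 to 0.08 SD too small (0.50 − 0.46 and 0.50 − 0.42), and power falls by 0.05 to 0.13 (0.48 − 0.43 and 0.48 − 0.35). Loss tied to the unseen Day 56 score can move the estimate by up to about 0.10 SD in either direction at 30% against 10%. The sampling SD is about 0.26, so none of this would dominate the result. With equal and similar loss in both arms there is no bias.

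Two stronger conclusions are tempting but unsupported: that the trial plans a completer-only analysis, and that false-positive risk is seriously inflated. The first contradicts the stated intent to treat. The second reaches only 0.066 in the least favourable null case run. The conflict and the unstated method stand whatever dropout proves to be; the sizes rest on the assumed rates, correlations and timing.

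**What to change.** 1. **Reconcile section 10.0 with Attachment 1.** For the primary outcome, state that the PANSS already listed under Visit 11/ET is obtained from every randomised subject who stops early and agrees, and that the reason is recorded if it is not done. For the safety assessments at exit, the two places must be reconciled; no particular rule is proposed here. The stopping criteria are not touched.
2. **Complete section 16.0.**
   - Name PANSS total at Visit 11 (Day 56) as the primary time point.
   - Use a repeated-measures likelihood model on Visits 4, 7 and 11, adjusted for baseline PANSS.
   - Assign an ET score to the nearest scheduled PANSS visit. Fix the rule before unblinding, including what happens if that visit already holds a score.
   - Keep all randomised subjects in the intent-to-treat set, report by arm those with no post-baseline PANSS, and include them in one not-at-random sensitivity analysis.

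**Cost.** One replaced sentence, one analysis paragraph and slightly more analysis work. No procedure outside Attachment 1 is added. If 10-20% of 40 leave (assumed), that is 0.10 × 40 = 4 to 0.20 × 40 = 8 exit PANSS ratings, and footnote d already lets them fall on a different day from the MRI. Loss driven by unseen scores will still leave some bias, which is why the sensitivity analysis is included.

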11.0 Laboratory Assessments

Study associated laboratory assessments (blood and urine) will be collected at time points specified in Study Procedures Table (Attachment 1) and analyzed by a local laboratory with the exception of the urine dipstick assessments which will be collected and analyzed onsite.

A total of 36 mL of blood will be collected for baseline/screening assessments (Visit 1) and 30 mL of blood (at each visit) will be collected at weeks 4 and 8 (Visits 7 and 11).

Laboratory assessments to be completed:

complete blood count with differential (CBC w/diff)
comprehensive metabolic panel (CMP)
magnesium
calcium
lipid panel
hemoglobin A1c (HgbA1c)
thyroid stimulating hormone level (TSH)
pregnancy test (serum (beta HCG) and urine)
varicella zoster titer (VZV titer)
urine toxicology screen
HIV test
hepatitis panel
plasma cytokines

Plasma cytokines

Research staff members will transport the cytokine specimens to Indiana Clinical and Translational Sciences Institute (CTSI) for processing and storage. Specimen handling procedures will be performed based on the CTSI standard operating procedures.

Assay Methodology:

Plasma cytokine and soluble receptor quantifications will be performed in duplicates using pre-validated commercially available assay kits employing Luminex® x-MAP technology. With this approach, we will be able to simultaneously quantify multiple human cytokines of relevance in a single experiment using very small volume of sample (Less than 50- μ l). Each of the assay kits employs 1-2 positive control(s) of known concentration and a negative control in every run. We will follow manufacturer provided established protocols for these assays. The testing panel for cytokines include IFN- γ , IL-10, IL-12p40, IL-12p70, IL-17, IL-1 β , IL-1ra, IL-2, IL-4, IL-6, and TNF- α (Millipore #HCYTOMAG-60K) and the testing panel for soluble receptors include soluble IL-2Ra, soluble IL-6R, soluble TNFRI and soluble TNFRII (Millipore HSCR-32K-04).

Luminex® is an antibody-based fluorescent immunoassay performed in suspension using distinctly identifiable bead sets. This platform uses internally color-coded microspheres (up to 100 distinct bead sets are available), for coating with a capture antibody specific for a target cytokine. The capability of adding multiple conjugated beads to each sample results in the ability to obtain multiple results from each sample. After the target cytokine from a test sample is captured by the bead, a biotinylated detection antibody is introduced. The reaction mixture is then incubated with Streptavidin-Phycoerythrin conjugate, the reporter molecule, to complete the reaction on the surface of each microsphere. The microspheres are allowed to pass rapidly through a laser which excites the internal dyes marking the microsphere set. A second laser excites PE, the fluorescent dye on the reporter molecule. Finally, high-speed digital-signal processors in the special reader instrument (Bio-Plex 200 system from Bio-Rad) identify each individual microsphere and quantify the result of its bioassay based on fluorescent reporter signals. A cytokine standard mix containing all target cytokines at known calibrated levels will be used to generate separate standard curves for each of the cytokines. Concentrations of each target cytokine will then be estimated using a standard curve specific to that particular cytokine by 5-parameter logistic curve fit method.

Preservation and Specimen Storage:

At the time of specimen submission to and processing by the CTSI the specimens will be stored in the freezers in specially labeled boxes, organized by internal “grids” for easy tracking. The bar-coded ID number and location of each specimen in the freezer will be entered and tracked by the CaTissue specimen database, a CTSI-maintained, password-protected database with limited access. No personal identifiers will appear on the blood tubes stored at the CTSI. The CTSI freezers will be secured and wired to an alarm system. The daily monitoring and maintenance of the freezers will be managed by the CTSI.

All study information will be stored in locked file cabinets and in password-protected computer files. Specimens will be stored by the Indiana CTSI on the IU campus but are not the property of the Indiana CTSI. The PI and IU will remain responsible for the specimens.

All specimens will be kept until they are used in their entirety.

